4.2.3. Exploratory endpoints

The exploratory objectives of this study are to provide preliminary evidence on kinetics of immune response for 3 doses (namely 5×10^{10} , 1×10^{11} and 2×10^{11} viral particles) of GRAd-COV2 either in healthy adults or in elderlies. Kinetics will be described as the variation of humoral and cellular immune response at time of enrollment and eventually at week 2, 4, 8, 12 and 24 after vaccination in each arm. Several T cells assay will be performed to identify T cell subset mainly involved in the response to vaccination and to evaluate their polyfunctionality and phenotypic profile. Level of Neutralizing antibodies (nAb) to GRAd32 will be measured in serum at time of enrollment, 4 and 24 weeks after vaccination to evaluate any potential impact on vaccination efficiency. A correlation between humoral and cellular immune response will be evaluated. Within-the-cohort comparisons will be carried out to assess difference in immune response according to different doses in the same population. Across-the-cohort comparison will be carried out to assess whether elderlies and adults have different pattern of immune response after vaccination at different end points.

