Figure 7 Estimated time (week) for enrollment and follow-up for Elderlies-Cohort. Figures within cells represent time (in weeks) after vaccination Grey bars represent timing of authorization for enrollment. Blue cells represent time of participants' enrollment. Emerald green cells represent time for safety assessment. Golden cells represent time of sampling carried out for immunogenicity assay on frozen specimens Red cells represent time of sampling carried out for immunogenicity assay on fresh samples. Orange cells represent milestones (letters represent the specific milestone). Olive green cells represent deliverables (numbers represent the specific deliverable).

5. Study design

This is a *first-in-human*, open-label, dose escalation, phase 1A/1B clinical trial to assess the safety and immunogenicity of the candidate GRAd-COV2 vaccine in healthy volunteers aged 18-55 years and elderly volunteers aged 65-85 years. The vaccine will be administered intramuscularly once in time.

We aim to enroll 90 patients in two cohorts with three arms each (i.e. 15 participants per arm in six arms). Each of the study arm will assess a unique dose of the candidate GRAd-COV2 in a particular population, either adults or elderlys.

- Adults-Cohort (Phase 1A):
 - Arm-1 will investigate safety and immunogenicity of a dose of 5×10^{10} viral particles in adults.
 - Arm-2 will investigate safety and immunogenicity of a dose of 1×10^{11} viral particles in adults.
 - Arm-3 will investigate safety and immunogenicity of a dose of 2×10^{11} viral particles in adults.
- Elderlies-Cohort (Phase 1B)
 - Arm-4 will investigate safety and immunogenicity of a dose of 5×10^{10} viral particles in elderlys.
 - Arm-5 will investigate safety and immunogenicity of a dose of 1×10^{11} viral particles in elderlys.
 - Arm-6 will investigate safety and immunogenicity of a dose of 2×10^{11} viral particles in elderlys.

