10.1. Sample size

This is a descriptive phase I first in human trial to assess safety and immunogenicity of three different vaccine doses. Overall, the trial will include 90 participants and no formal sample size calculation is carried out.

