10.2. Statistics analysis

This is a descriptive safety study, where participants will be vaccinated with different doses of GRAd-COV2 against SARS-CoV-2. Forty-five participants per age cohort (for a total of 90 subjects) will be vaccinated in total. This sample size should allow an estimation to be made of the frequency and magnitude of outcome measures, rather than aiming to obtain formal statistical significance for differences between groups.

Safety data will be presented according to frequency, severity and duration of adverse events. The primary analysis for immunogenicity will be to assess the difference in magnitude of SARS-CoV-2 specific T-cell and antibody responses between the groups. We will assess vaccine immunogenicity by comparing the change in these immunological parameters from baseline to different endpoints. At the end of the study, we expect to

6 measures per participant for T-cell response and antibody level. We will explore the possibility to describe kinetics of these parameters through non-parametric test for comparison of:

- A. *within-the-arm medians* at different times (i.e. baseline vs. either week-2, week-4, week-8, week-12 and week 24) between groups at different follow-up time);
- B. *within the Adults-Cohort medians* at specific time (i.e. Arm-1 vs. either Arm-2 or Arm-3 at baseline, week-2, week-4, week-8, week-12 or week-24).
- C. *within the Elderlies-Cohort medians* at specific time (i.e. Arm-4 vs. either Arm-5 or Arm-6 at baseline, week-2, week-4, week-8, week-12 or week-24).
- D. *Across the cohort medians at specific time* (i.e. Arm-1 vs. Arm-4; Arm-2 vs Arm-5; Arm-3 vs. Arm-6 at baseline, week-2, week-4, week-8, week-12 or week-24)

Explorative kinetics model based on regression techniques for correlated measures will be carried out if normal distribution of data is proven.

11. Data Management

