## 1 INTRODUCTION

The analyses described in this SAP are based upon the following study documents:

- Study Protocol, Version 2.0 (September 8, 2020)
- electronic Case Report Form (eCRF), Version 4 (generated on August 4, 2020)
- DSMB Charter, Version 2.0

Per protocol, the collected data will be analyzed and reported in three steps according to stages achieved during the course of the study, ie:

Delivery 1: Interim Analysis 1

A report on safety and immunogenicity at 4 weeks for Adults-Cohort will be developed; this report will include:

- a. an analysis of safety issue in the three adults-arms;
- b. pivotal considerations for authorizing enrollment in the Elderlies-Cohort;
- c. a preliminary analysis of immunogenicity in the three adults-arms aimed at identifying the most convenient dose to be used in the eventual phase 2/3 trial.

Delivery 2: Interim Analysis 2

A report on safety and immunogenicity at 4 weeks for Elderlies-Cohort will be developed; this report will include pivotal considerations on:

- a. an analysis of safety issues in the three elderlies-arms
- b. a preliminary analysis of immunogenicity in the three elderlies-arms aimed at identifying the most convenient doses to be used in the eventual phase 2/3 trial.
- c. comparison of safety and immunogenicity between adults and elderlies (across the cohort comparison) to define the most convenient dose to be used either in general population or special groups at risk.

Delivery 3: Final Analysis

Within one year since LSLV final report will be produced including:

- a. Final analysis on safety and immunogenicity at 24 weeks after vaccination in Adults-Cohort
- b. Final analysis on safety and immunogenicity at 24 weeks after vaccination in Elderlies-Cohort

Analyses described hereafter will cover all these three stages of the study with applicable closures on selected analyses if a stage requires.

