**Table 3 Grouping: Safety (excluding AEs and Categorical Safety), Immunogenicity, Labs and Diary Data**

Delivery						
IA 1	Arm-1	Arm-2	Arm-3			
IA 2	Arm-4	Arm-5	Arm-6			
FA	Arm-1	Arm-2	Arm-3	Arm-4	Arm-5	Arm-6

IA: Interim analysis. FA: Final analysis.

For interest of space table displays treatment arms instead of treatment labels, but outputs will display treatment labels.

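### For immunogenicity, the adult-versus-elderly question is planned only as three separate 15-v-15 arm pairs, with no combined estimate stratified by dose

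*Protocol*

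**What the plan says.** The age question appears in three places. Protocol 4.2.3 says "Across-the-cohort comparison will be carried out to assess whether elderlies and adults have different pattern of immune response". Protocol 4.2.5 (deliverable 2c) and SAP section 1 (Interim Analysis 2) promise a "comparison of safety and immunogenicity between adults and elderlies (across the cohort comparison) to define the most convenient dose".

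The layout is balanced. Protocol section 5 plans two cohorts given the same three doses, "i.e. 15 participants per arm in six arms", and Protocol 10.2 confirms "Forty-five participants per age cohort (for a total of 90 subjects) will be vaccinated in total".

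For the analysis, Protocol 10.2 makes the between-group difference in response magnitude the main immunogenicity analysis. For age it then lists "Arm-1 vs. Arm-4; Arm-2 vs Arm-5; Arm-3 vs. Arm-6 at baseline, week-2, week-4, week-8, week-12 or week-24". It also allows an exploratory regression model for kinetics, conditional on normality and with no age or dose term named.

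SAP 4.10 summarises immunogenicity by visit and treatment group, using the columns of Table 3, titled "Grouping: Safety (excluding AEs and Categorical Safety), Immunogenicity, Labs and Diary Data". Those columns are single arms, with no cohort totals. SAP Table 2 does have adult and elderly totals at the final analysis, but for adverse events and categorical safety only.

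**The concern.** The stated question concerns the two age groups, while the planned answer is three separate answers, one per dose. Nothing says how to read them together. If the age effect is much the same at every dose, the three results can still disagree by chance, and each is much less precise than the 90 participants allow. Calling an age difference whenever any one pair reaches significance would also raise the false-positive rate. The comparison matters because deliverable 2c uses it to choose phase 2/3 doses for the general population and for groups at risk.

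**Working it through.** **The plan's own figure.** 6 arms x 15 = 90, and 3 x 15 = 45 per cohort, as stated. Protocol 10.1 says "no formal sample size calculation is carried out", so there is no power or precision figure to reproduce.

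**Assumptions not in the documents.** Log10 SD 0.5 (range 0.3 to 0.7), common to all arms; two-sided 0.05; no missing data; the same age effect at each dose unless stated.

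**Standard error of the adult-elderly difference**, SE = SD x sqrt(2/n):
- one arm pair, n = 15: 0.365 SD
- all three doses, stratified, n = 45: 0.211 SD
- ratio 0.211/0.365 = 1/sqrt(3) = 0.58, so 42% smaller

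**95% CI factor** = 10^(t x SD x sqrt(2/n)), with t = 2.048 (28 df) for one pair and t = 1.989 (84 df = 90 - 6 arms) for the stratified estimate. At SD 0.5, the pair gives 10^(2.048 x 0.5 x 0.365) = 2.37 and the stratified estimate gives 10^(1.989 x 0.5 x 0.211) = 1.62.

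| log10 SD | One pair | Stratified by dose |
|---|---|---|
| 0.3 | 1.68 | 1.34 |
| 0.5 | 2.37 | 1.62 |
| 0.7 | 3.34 | 1.97 |

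**What three separate tests would show.** Take a true 2-fold difference at every dose and SD 0.5, so the shift is 0.301/0.5 = 0.60 SD. By simulation, one Mann-Whitney test of 15 v 15 has about 32% power. Then:
- all three miss: 0.68^3 = 31%
- all three positive: 0.32^3 = 3%
- split (one or two positive): the remainder, about 66% by simulation
- the van Elteren test stratified by dose has about 78% power, so it misses in about 22%

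**No true difference.** At least one of the three tests is positive in about 12.5% of simulated trials, against 4.8% for the stratified test.

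**When the common-effect assumption fails.** With a 1 SD age effect at one dose only, that arm pair detects it in about 71% of trials and the stratified test in about 28%. The contrast between the age effects at two doses has SE = sqrt(4/15) = 0.52 SD. The interaction detectable with 80% power is therefore 2.80 x 0.516 = 1.45 SD. At SD 0.5 that is 10^(0.72), about a 5-fold ratio of ratios.

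**The case against.** The strongest reply is that the study is descriptive. Protocol 10.2 says its size serves estimation, "rather than aiming to obtain formal statistical significance for differences between groups"; Protocol 4.2.3 classes these comparisons as exploratory; and SAP 4.13 plans no formal testing. This stands against treating the point as a power failure. It does not remove the point, because precision is the right measure for an estimation study and that is where the gain lies.

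Three stronger readings are tempting, and the documents do not support them.

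- *The plan discards most of its data.* It does not. The three age pairs together use all 90 participants, and SAP Table 2 already pools adverse events by cohort at the final analysis. What is missing is the combined immunogenicity estimate. The regression model in Protocol 10.2 could in principle supply one, but it names no such term and the SAP does not carry it forward.
- *The dose comparisons have the same weakness and should be pooled over age.* Protocol 4.2.3 asks about dose differences within the same population, and deliverables 1c and 2b seek doses separately for adults and for the elderly. A within-cohort dose pair already uses every participant relevant to it. Neither document asks for an age-averaged dose effect or for adverse-event columns pooled by dose.
- *Power rises from 32% to 78%.* That sets one arm test against the combined test. The fair comparison for a missed effect is all three tests missing, 31%, against 22%. At SD 0.7 it is 0.82^3 = 55% against 52%.

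Two further objections stand as limits. The gain needs a roughly common age effect across doses. Arms are also enrolled sequentially without randomisation, with elderly enrolment waiting for 4-week adult safety data. A narrower interval is thus no less confounded with calendar time, a weakness the arm pairs share.

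**Conclusion.** The point holds for age and immunogenicity. Both documents pose an adult-versus-elderly question, the design is balanced to answer it, and neither specifies a combined estimate. If the effect is similar across doses, stratifying cuts the standard error by 42% against one arm pair and gives one answer where three tests would usually split. The sizes rest on the assumed SD, complete data and a common effect.

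This is an optional precision gain in a descriptive phase 1 study. No stated figure is wrong, and no change to the dose comparisons or to the adverse-event columns follows.

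**What to change.** In SAP 4.10, for anti-S and neutralising antibody at week 4 and ELISpot at week 2, once data from both cohorts are available, add:

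1. the adult/elderly ratio with 95% CI, adjusted for dose, on the log scale;
2. the van Elteren test stratified by dose as its rank-based companion, because SAP 4.10 sets values below the limits to 1.9 (anti-S) and 5 (neutralisation titre), and a log-scale ratio is sensitive to such floor values;
3. the three arm-level age comparisons, kept and shown beside the combined result.

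SAP section 1 places the cross-cohort comparison at Interim Analysis 2, but Table 3 and SAP 4.14 limit that analysis to Arms 4 to 6. The new text should say that the adult data are brought in.

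The cost is a few lines of SAP text and code, with no new data. State three limits with the result: the ratio is an average over doses and can hide an age effect at a single dose; the age-by-dose interaction is too imprecise to rule that out; and the contrast remains confounded with calendar time.

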11.1. Quality Control and Source Data Verification

All subject data relating to the study will be recorded on electronic case report form (eCRF). The local investigator (physician) is responsible for verifying that data entries are accurate and correct by physically or electronically signing the eCRF. The Investigator shall assure the accuracy, completeness, legibility, and timeliness of the data reported on the eCRFs and in all required reports.

The Investigator must maintain accurate documentation (source data) that supports the information entered in the eCRF. The Investigator must permit study-related monitoring, audits, Ethical committee review, and regulatory agency inspections and provide direct access to source data documents.

Study monitors will perform ongoing source data review of data to confirm that data entered into the eCRF by authorized site personnel are accurate, complete, and verifiable from source documents; that the safety and rights of subjects are being protected and that the study is being conducted in accordance with the currently approved protocol and any other study agreements, 21 CFR, ICH-GCP, and all applicable regulatory requirements.

Records and documents, including signed ICF, pertaining to the conduct of this study must be retained by the Investigator for 15 years after study completion unless local regulations or institutional policies require a longer retention period. No records may be destroyed during the retention period without the written approval of the Sponsor. No records may be transferred to another location or party without written notification to the Sponsor.

All data generated by the site personnel will be captured electronically at each study center using eCRF. Once the eCRF clinical data have been submitted to the central server at the independent data center, corrections to the data fields will be captured in an audit trail. The reason for change, the name of the person who performed the change, together with the time and date will be logged to provide an audit trail.

If additional corrections are needed, the responsible monitor or data manager will raise a query in the eCRF. The appropriate staff at the study site will answer queries sent to the Investigator. The name of the staff member responding to the query, and time and date stamp will be captured to provide an audit trail. Once all source data verification is complete and all queries are closed, the eCRF page will be 'frozen' to prevent further changes.

The specific procedures to be used for data entry and query resolution using the eCRF will be provided to study sites in a training manual. In addition, site personnel will receive training on the eCRF.

11.2. Audit / Inspection

The Agenzia Italiana del Farmaco the National Ethical committee for COVID and the Sponsor's Clinical Quality Assurance Group may complete audit / inspections any time to assess compliance with the protocol and the principles of Good Clinical Practice and all other relevant regulations.

Clinical centers and principal investigator must permit study-related monitoring, audits, Ethical committee review and regulatory agency inspections and provide direct access to source data documents; they will be carried out giving due consideration to data protection and medical confidentiality. The Investigator always assures the Sponsor and designated representatives of the necessary support.

11.3. Monitoring and Access to Source Data

During study conduct, monitoring will be performed by a Contract Research Organization (CRO). The CRO will conduct periodic monitoring, via telephone contacts and on-site visits (where applicable), to ensure that the protocol and guidelines are being followed.

During the on-site visits the monitors may review source documents to confirm that the data recorded on the eCRFs are accurate, with a focus on ICF and other relevant study data.

It is important that the physician(s) and their relevant personnel are available during the monitoring visits or during the phone contacts.

Checking of the eCRF entries for completeness and clarity, and cross-checking with source documents, will be required to monitor the progress of the study.

11.4. Data collection

Subjects will be identified by a subject number, assigned at the screening visit.

The data will then be processed, evaluated, and stored in pseudonymised form in accordance with applicable data protection regulations.

11.4.1. Data Management

The Clinical Research Organization (CRO) contracted for this study will be responsible for the study data management, which will process the data in accordance with procedures approved by the Sponsor, including data validation, resolution of errors, and quality control of defined immunogenicity analysis and safety variables.

11.4.2. Case Report Form(eCRF)

The eCRFs will be used to capture all the data related to the study. The eCRFs use third party software (Rave[®]) to capture data via an on-line system on a computer.

Data related to the study will be recorded electronically in a central database over encrypted lines, and all entries and modifications to the data will be logged in an audit trail. Access to the system will only be granted after appropriate and documented training.

The data will be entered in the system from the source data according to the description and timelines specified in the eCRF Completion Guidelines.

Subjects/patients that fail screening will be noted as a screen failure in the eCRF. Screen failures are participants who consent to participate in the clinical study but are not subsequently entered in the study. A minimal set of screen failure information is required to ensure transparent reporting of screen failure participants to meet the Consolidated Standards of Reporting Trials (CONSORT) publishing requirements and

to respond to queries from regulatory authorities. Minimal information includes demography, screen failure details, eligibility criteria, and any SAEs.

Electronic signatures will be used where signatures are required on pages and/or visits. Automated data entry checks will be implemented where appropriate; other data will be reviewed and evaluated for accuracy by the CRA.

All entries, corrections, and changes must be made by the investigator or a designee.

11.4.3. Database Release

The database will be declared to be complete and accurate by mutual agreement between the CRO and the Sponsor. Once the database release has been approved by both parties, the database will be released in accordance with the CRO's procedure, as agreed by the Sponsor.

If a site closes before the study has been completed, the investigator will continue to have read-only access to the eCRF until the study has been completed. At database release, all user access to the eCRF will be changed to read-only. Renewed access to the eCRF will be given if corrections or updates to the released Rave® database are required. At the end of the study, the site(s) will be provided with all data related to the site (including eCRF data, queries, and the audit trail) using a secure electronic medium; the secure storage of these data at the site is the responsibility of the investigator. When confirmation of receipt of the data has been received from all site(s), all user access to the eCRF will be revoked. If, for some reason, the data are not readable for the full retention period 15 years or in accordance with national requirements, whichever is longer), the investigator may be requested that the data be re-sent.

11.5. Source Documents

Source documents provide evidence for the existence of the subject and substantiate the integrity of the data collected. Source documents are filed at the Investigator's site.

Data entered in the eCRF that are transcribed from source documents must be consistent with the source documents or the discrepancies must be explained. The Investigator may need to request previous medical records or transfer records, depending on the study. Also, current medical records must be available.

13.1. Data safety monitoring board (DSMB)

DSMB will include 4 voting members and 2 technical supporting members.

The chair of the board and the 3 other voting members will be independent experts with no connection either with sponsor or clinical centers participating to the study. To participate to the board each member should disclose any potential conflict of interest according to Italian legislation.

The decisions of DSMB are provided according to the time framework reported in milestone (section 4.2.2). These decisions are binding so that enrolment of each eventual group of participants cannot be carried out without the advice of DSMB. The board has the power to withhold the enrollment and terminate the study.

In case the enrollment is withheld because a halting rule is met, the DSMB will provide binding advice on how and when the study enrollment can be restarted, or the study should be terminated.

Principal investigator may seek the advice of DSMB in case local investigator report the occurrence of special situation that do not immediately meet criteria for halting rules.

The DSMB will meet once a week throughout the enrollment of participants and once a month after the end of the enrollment.

DSMB may seek the advice of ethical committee if in case local investigator or principal investigator report the occurrence of special situation that do not immediately meet criteria for halting rules.

Significant variation to the study design that are proposed after the approval of the study should be approved by DSMB and by ethical committee.

